Sex	Female (reference)	-	-	-	-
	Male	xxx.x	xxx.x	xx.x-xx.x	x.xxx
BMI	<30 (reference)	-	-	-	-
	≥30	xxx.x	xxx.x	xx.x-xx.x	x.xxx
Prior Receipt of Influenza Vaccine	Did Not Receive 2016-2017 Seasonal Influenza Vaccine (reference)	-	-	-	-
	Received 2016-2017 Seasonal Influenza Vaccine	xxx.x	xxx.x	xx.x-xx.x	x.xxx

N = XX (Number of subjects in the Per Protocol Population)
n = XX (number of subjects with results available at 21 days post IIV4 vaccination in the per protocol population).
XX subjects missing covariate data were excluded from this analysis.

Tables with similar format:

Table 93: Multiple Linear Regression Model to Evaluate the Relationship of Administration Schedule with Log-Adjusted HAI Titer at 180 Days Post Second Dose of AS03 adjuvanted A/H7N9 Vaccine, Adjusted for Baseline Covariates, Per Protocol Population

Table 94: Multiple Linear Regression Model to Evaluate the Relationship of Administration Schedule with Log-Adjusted Neut Titer at 21 Days Post Second Dose of AS03 adjuvanted A/H7N9 Vaccine, Adjusted for Baseline Covariates, Per Protocol Population*

Table 95: Multiple Linear Regression Model to Evaluate the Relationship of Administration Schedule with Log-Adjusted Neut Titer at 180 Days Post Second Dose of AS03 adjuvanted A/H7N9 Vaccine, Adjusted for Baseline Covariates, Per Protocol Population

Table 96: Multiple Linear Regression Model to Evaluate the Relationship of Administration Schedule with Log-Adjusted HAI Titer against Seasonal IIV4 Strains at 21 Days Post IIV4 Vaccination, Adjusted for Baseline Covariates, Per Protocol Population*

Model Parameter		Parameter Estimate	SE	95%CI	p-value
A/Michigan/45/2015 X-275 (H1N1)					
Intercept	N/A	xxx.x	xxx.x	-	x.xxx
Treatment	Simultaneous Administration (reference)	-	-	-	-
	Sequential Administration	xxx.x	xxx.x	xx.x-xx.x	x.xxx
	IIV4 Only	xxx.x	xxx.x	xx.x-xx.x	x.xxx
Age (years)	N/A	xxx.x	xxx.x	xx.x-xx.x	x.xxx
Sex	Female (reference)	-	-	-	-
	Male	xxx.x	xxx.x	xx.x-xx.x	x.xxx
BMI	<30 (reference)	-	-	-	-
	≥30	xxx.x	xxx.x	xx.x-xx.x	x.xxx
Prior Receipt of Influenza Vaccine	Did Not Receive 2016-2017 Seasonal Influenza Vaccine (reference)	-	-	-	-
	Received 2016-2017 Seasonal Influenza Vaccine	xxx.x	xxx.x	xx.x-xx.x	x.xxx
[Repeat for all IIV4 Strains]					
N = XX (Number of subjects in the Per Protocol Population) n = XX (number of subjects with results available at 21 days post IIV4 vaccination in the per protocol population). XX subjects missing covariate data were excluded from this analysis.					

Tables with similar format:

- Table 97: Multiple Linear Regression Model to Evaluate the Relationship of Administration Schedule with Log-Adjusted HAI Titer against Seasonal IIV4 Strains at 180 Days Post IIV4 Vaccination, Adjusted for Baseline Covariates, Per Protocol Population**
- Table 98: Multiple Linear Regression Model to Evaluate the Relationship of Administration Schedule with Log-Adjusted Neut Titer against Seasonal IIV4 Strains at 21 Days Post IIV4 Vaccination, Adjusted for Baseline Covariates, Per Protocol Population**
- Table 99: Multiple Linear Regression Model to Evaluate the Relationship of Administration Schedule with Log-Adjusted Neut Titer against Seasonal IIV4 Strains at 180 Days Post IIV4 Vaccination, Adjusted for Baseline Covariates, Per Protocol Population**

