8.1 Screening (Optional) and Enrollment Visits, All Groups

8.1.1 Visit 00, Screening Clinic Visit (Optional) (Day -28 to -1)

- Subjects will be provided with a description of this trial (purpose and study procedures) and asked to read and sign the ICF. The ICF will be signed prior to performing any study procedures, including administration of the first and second study vaccinations for Group 1, and the first study vaccination for Groups 2 and 3.
- Demographic information will be obtained by interview of subjects.
- Eligibility criteria will be reviewed with subjects.
- Complete medical history will be obtained by interview of subjects to ensure eligibility.
- All concomitant medications taken within 60 days prior to signing the ICF will be reviewed with subjects to determine stability of chronic diseases and eligibility. Medications reported in the eCRF are limited to those taken within 30 days prior to the first study vaccination.
- Subject receipt of licensed seasonal influenza vaccine over the previous two seasons, what type (inactivated or live attenuated), and approximate date of vaccination will be recorded on the appropriate DCF, if known. Prior receipt of licensed seasonal influenza vaccine in the 2017/2018 season is exclusionary (see [Section 5.1.2](#)).
- Subject receipt of non-seasonal influenza vaccines, including those that are experimental, what type (inactivated or live attenuated), what subtype (e.g., A/H3, A/H5, A/H9) and approximate date of vaccination will be recorded on the appropriate DCF, if known. Prior receipt of non-seasonal influenza vaccines are not exclusionary, except influenza A/H7 vaccines (see [Section 5.1.2](#)).
- Vital signs, including oral temperature, pulse, and blood pressure, will be obtained to ensure eligibility prior to first study vaccination. Subjects must not eat or drink anything hot or cold, or smoke within 10 minutes prior to taking oral temperature.
- Height and weight will be collected for the calculation of BMI.

- A physical examination will be performed on all subjects to include the following organs and organ systems: skin, head and neck, lungs, heart, liver, spleen, extremities, lymph nodes, abdomen, general appearance, musculoskeletal and nervous system and as assessment for signs suggestive of a PIMMC, by a study clinician licensed to make medical diagnoses and listed on the Form FDA 1572 as the site principal investigator or sub-investigator.

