6.4. Covariates and Subgroups

As a protocol defined exploratory analysis, HAI antibody response following the second vaccination will be summarized stratified by the following covariates: age (categorical: 19-34, 35-49, 50-64), sex (male, female), body mass index (<30 , ≥ 30), and prior receipt of seasonal influenza vaccine(s) (received 2016-2017, did not receive 2016-2017, unknown), and these covariates will be considered in statistical modeling as described in Section 8.3. As these analyses are exploratory the study was not powered for any subgroup analyses.

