transformation, multiple linear regression will be fit to examine the relationship of log transformed titers at 21 or 180 days after the dose of interest (second dose of AS03 adjuvanted A/H7N9 IIV for the 2017 A/H7N9 strain; IIV4 vaccination for the seasonal IIV4 strains) with treatment schedule. All models will be fit with and without adjustment for the following covariates (Z): age in years, sex (female, male), BMI (<30 , ≥ 30), and prior receipt of seasonal influenza vaccine (did not receive 2016-2017 seasonal vaccine, received 2016-2017 seasonal vaccine). The models as shown below assume a linear relationship between age in years and both probability of seroconversion and GMT. The validity of this assumption will be assessed prior to analysis and, if the relationship between age and response is found to be non-linear, adjustments will be made to model parameters to satisfy regression assumptions. Modeling assumptions will be checked using standard diagnostic methods (e.g., using the INFLUENCE option in PROC LOGISTIC or PROC GLM). Parameter estimates and odds ratio estimates for the logistic models will be presented for the 2017 A/H7N9 strain without covariate adjustment in [Table 68](#), [Table 69](#), [Table 70](#), [Table 71](#), and with covariate adjustment in [Table 76](#), [Table 77](#), [Table 78](#), [Table 79](#); and for the seasonal IIV4 strains without covariate adjustment in [Table 72](#), [Table 73](#), [Table 74](#), [Table 75](#), and with covariate adjustment in [Table 80](#), [Table 81](#), [Table 82](#), [Table 83](#). Parameter estimates for the multiple linear regression models will be presented for the 2017 A/H7N9 strain without covariate adjustment in [Table 84](#), [Table 85](#), [Table 86](#), [Table 87](#), and with covariate adjustment in [Table 92](#), [Table 93](#), [Table 94](#), [Table 95](#); and for the seasonal IIV4 strains without covariate adjustment in [Table 88](#), [Table 89](#), [Table 90](#), [Table 91](#), and with covariate adjustment in [Table 96](#), [Table 97](#), [Table 98](#), [Table 99](#).

Model 1A: Logistic Regression (without covariate adjustment):

$$\text{logit}[P(\text{seroconversion})] = \beta_0 + \beta_1 \times \text{Treatment} + \varepsilon$$

Model 1B: Logistic Regression (with covariate adjustment):

$$\text{logit}[P(\text{seroconversion})] = \beta_0 + \beta_1 \times \text{Treatment} + \beta_2 \times Z + \varepsilon$$

Model 2A: Multiple Linear Regression (without covariate adjustment):

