$$\log(\text{titer}) = \beta_0 + \beta_1 \times \text{Treatment} + \varepsilon$$

Model 2B: Multiple Linear Regression (with covariate adjustment):

$$\log(\text{titer}) = \beta_0 + \beta_1 \times \text{Treatment} + \beta_2 \times Z + \varepsilon$$

Subjects missing data for one or more covariates will be excluded from Models 1B and 2B.

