9.1. Demographic and Other Baseline Characteristics

Summaries of age, sex, ethnicity, race, BMI, and prior receipt of seasonal influenza vaccine will be presented by site ([Table 23](#), [Table 24](#)) and by treatment group ([Table 25](#), [Table 26](#)). Age will be summarized as a continuous variable. Ethnicity is categorized as Hispanic or Latino, or not Hispanic and not Latino. In accordance with NIH reporting policy, subjects may self-designate as belonging to more than one race or may refuse to identify a race, the latter reflected in the electronic case report form (eCRF) as “No” to each racial option. BMI will be summarized as a continuous as well as categorical variable, categorized as (<30, ≥30). Self-reported history of prior receipt of seasonal influenza vaccine will be categorized as follows: received 2016-2017 seasonal vaccine, did not receive 2016-2017 seasonal vaccine, or unknown. Demographic information for individual subjects will be provided in [Listing 6](#). Subjects’ prior influenza vaccination history (seasonal and non-seasonal) will be provided in [Listing 8](#).

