N = XX (Number of subjects in the Per Protocol Population)
n = XX (number of subjects with results available at 21 days post second dose of AS03 adjuvanted A/H7N9 IIV in the per protocol population).
XX subjects missing covariate data were excluded from this analysis.

Tables with similar format:

Table 69: Logistic Regression Model to Evaluate the Relationship of Administration Schedule with HAI Seroconversion Against 2017 A/H7N9 at 180 Days Post Second Dose of AS03 adjuvanted A/H7N9 Vaccine, Per Protocol Population *

Table 70: Logistic Regression Model to Evaluate the Relationship of Administration Schedule with Neut Seroconversion Against 2017 A/H7N9 at 21 Days Post Second Dose of AS03 adjuvanted A/H7N9 Vaccine, Per Protocol Population

Table 71: Logistic Regression Model to Evaluate the Relationship of Administration Schedule with Neut Seroconversion Against 2017 A/H7N9 at 180 Days Post Second Dose of AS03 adjuvanted A/H7N9 Vaccine, Per Protocol Population

Table 72: Logistic Regression Model to Evaluate the Relationship of Administration Schedule with HAI Seroconversion Against Seasonal IIV4 Strains at 21 Days post IIV4 Vaccination, Per Protocol Population*

Model Parameter	Parameter Category	Parameter Estimate	SE	p-value	Odds Ratio	95%CI
A/Michigan/45/2015 X-275 (H1N1)						
Intercept	N/A	xxx.x	xxx.x	x.xxx	-	-
Treatment	Simultaneous Administration (reference)	-	-	-	-	-
	Sequential Administration	xxx.x	xxx.x	x.xxx	xx.x	xx.x-xx.x
	IIV4 Only	xxx.x	xxx.x	x.xxx	xx.x	xx.x-xx.x
[Repeat for all IIV4 Strains]						
N = XX (Number of subjects in the Per Protocol Population) n = XX (number of subjects with results available at 21 days post IIV4 vaccination in the per protocol population). XX subjects missing covariate data were excluded from this analysis.						

Tables with similar format:

Table 73: Logistic Regression Model to Evaluate the Relationship of Administration Schedule with HAI Seroconversion Against Seasonal IIV4 Strains at 180 Days Post IIV4 Vaccination, Per Protocol Population

Table 74: Logistic Regression Model to Evaluate the Relationship of Administration Schedule with Neut Seroconversion Against Seasonal IIV4 Strains at 21 Days Post IIV4 Vaccination, Per Protocol Population*

Table 75: Logistic Regression Model to Evaluate the Relationship of Administration Schedule with Neut Seroconversion Against Seasonal IIV4 Strains at 180 Days Post IIV4 Vaccination, Per Protocol Population

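### The unadjusted regression shells exclude subjects for missing covariates, against SAP 8.3.2, and the adjusted models have no level for unknown prior vaccination

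*SAP*

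**What the plan says.** SAP Section 8.3.2 plans logistic models for seroconversion and linear models for log titer, each fitted with and without covariates, in the per-protocol (PP) population. Models 1A and 2A contain treatment only. Models 1B and 2B add age, sex, BMI group and prior seasonal vaccination. The rule on missing covariates reads: "Subjects missing data for one or more covariates will be excluded from Models 1B and 2B".

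The table shells in SAP Section 14.2.1 differ. Under Tables 68, 72, 84 and 88, which show the treatment-only models, the footnote reads "XX subjects missing covariate data were excluded from this analysis". Tables 69-71, 73-75, 85-87 and 89-91 take their format from these four.

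Prior vaccination is defined in two ways:

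- Section 6.4 lists "received 2016-2017, did not receive 2016-2017, unknown" and sends its covariates to the modelling in Section 8.3.
- Section 9.1 lists "received 2016-2017 seasonal vaccine, did not receive 2016-2017 seasonal vaccine, or unknown", and baseline Tables 23 and 25 have an Unknown row.
- Section 8.3.2 gives the model covariate as "prior receipt of seasonal influenza vaccine (did not receive 2016-2017 seasonal vaccine, received 2016-2017 seasonal vaccine", which is two levels. The adjusted shells (Tables 76, 80, 92, 96) and the stratified shells (Tables 60, 64) also have two.

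Section 6.5 rules out imputation and expects little missing data.

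**The concern.** A programmer working from the shells and one working from the text would fit the unadjusted models on different subjects. Nothing in a treatment-only model calls for dropping someone whose vaccination history is unknown.

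The second mismatch decides who counts as missing. Age, sex, height and weight are collected on everyone. Vaccination history is self-reported (SAP 9.1) and recorded only if known (Protocol 8.1.1 and 8.1.3), so it is the covariate most likely to be incomplete. The SAP foresees this with an *unknown* category and then leaves that category out of the models.

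These regressions are the plan's only models that estimate and test the effect of schedule on immune response. They sit in the exploratory section, but Section 8.1 cites them from the primary analysis. Their lead tables are starred for the preliminary report, whose analyses count as final under Section 6.2.1. The ambiguity should therefore be settled before that report.

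**Working it through.** No printed figure is in dispute. The minimum detectable differences in Protocol Tables 5 and 6 (repeated as SAP Tables 10 and 11) reproduce to within 0.01 under two-sided likelihood-ratio power at 50 vs 50 and 75 vs 50.

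**Step 1: text against shells.**

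| Model | Covariates | Exclusion in 8.3.2 | Exclusion in shell |
|---|---|---|---|
| 1A, 2A (Tables 68-75, 84-91) | none | none | yes |
| 1B, 2B (Tables 76-83, 92-99) | four | yes | yes |

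The rows for 1A and 2A conflict. The rows for 1B and 2B agree.

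**Step 2: where an *unknown* subject goes.** The model factor has two levels, no value is imputed (6.5), and a subject without a usable covariate leaves Models 1B and 2B (8.3.2). Deletion is the only route these rules provide. This is an inference, because no sentence equates *unknown* with missing. In Tables 60-67 the subject has no row to appear in.

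**Step 3: consequences, one alternative at a time.**

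- Shells followed: the unadjusted and adjusted models share one complete-case set, but the unadjusted models have lost subjects for no reason.
- Text followed: the unadjusted models keep every PP subject with a result, and the adjusted models rest on fewer. A difference between the two estimates then mixes covariate adjustment with a change of subjects.

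**Step 4: size.** The share unknown, u, is not in the documents; 2% to 10% is an assumption. Protocol 11.4.2 plans for about 50 PP subjects in each of Groups 1 and 2 (60 × 0.85 = 51). With equal loss in both groups, n becomes 50(1 − u) and the standard error is multiplied by 1/√(1 − u):

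| u | n per group | SE multiplier | Rise |
|---|---|---|---|
| 2% | 49 | 1/√0.98 = 1.010 | 1.0% |
| 5% | 47.5 | 1/√0.95 = 1.026 | 2.6% |
| 10% | 45 | 1/√0.90 = 1.054 | 5.4% |

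**Step 5: what a third level recovers.** In a linear model with treatment and a stratum factor, information on the treatment effect adds over strata as n₁n₂/(n₁ + n₂). With 45 + 45 known and 5 + 5 unknown, that is 45 × 45/90 + 5 × 5/10 = 22.5 + 2.5 = 25, the same as 50 × 50/100 = 25. This is full recovery when the unknown subjects are evenly split. If all of them fall in one group, that stratum adds nothing, and the result is as with deletion.

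**The case against.** The footnote is most simply a template carry-over. The same line stands under the adjusted tables, where it belongs, and the count is a placeholder. That explains the conflict but does not remove it, since the shells are what gets programmed.

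Section 6.4 lists *unknown* and says its covariates go into the models, so three levels may have been intended. That stands to this extent: deletion must be stated as an inference.

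One could also run both models on a common complete-case set on purpose. That is coherent, but Section 8.3.2 does not say it, and it discards results.

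A reader might infer more than the documents support:

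- *That the comparisons both lose subjects needlessly and rest on different sets.* For the unadjusted and adjusted pair these are alternatives, as Step 3 shows.
- *That the planned detectable differences are eroded.* Protocol Tables 5 and 6 describe an unadjusted two-group comparison, not the adjusted models. Under the text of 8.3.2 the unadjusted model loses no one.
- *That the vaccination and BMI covariates are miscoded.* Sites do record "Subject receipt of licensed seasonal influenza vaccine over the previous two seasons", but Sections 6.4 and 8.3.2 prespecify the 2016-2017 season and a BMI cut at 30. The reference level says only that the 2016-2017 vaccine was not received, which is accurate. Using two seasons or continuous BMI would be a preference, not a correction.

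**Conclusion.** Two inconsistencies stand. The footnote under the unadjusted shells contradicts Section 8.3.2, and *unknown* prior vaccination is a defined category with no place in the adjusted models or in Tables 60-67. The first is explicit. The second rests on reading the two-level factor together with the missing-covariate rule and the absence of imputation.

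The effect is confined to the PP regressions and the stratified tables. The primary immunogenicity analysis is the mITT summary (Section 8.1), which loses no one for an unknown covariate. The size depends on a share that the documents do not give. At an assumed 2% to 10%, equal across groups, the standard error rises by about 1% to 5%. At the low end, where the SAP expects missing data to lie, this is negligible. The correction is worth making because the analysis set is undefined until it is made, not because a large loss has been shown.

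**What to change.** 1. Delete the exclusion footnote from Tables 68-75 and 84-91, so that Models 1A and 2A use every PP subject with a result, as Section 8.3.2 says.
2. In Models 1B and 2B, enter prior vaccination with the three levels of Section 6.4 (received, did not receive, unknown). Amend the covariate list in 8.3.2, and add the *unknown* row to Tables 60-67, 76-83 and 92-99.

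The cost is SAP wording and shell edits, with no new data. The adjusted models spend one more degree of freedom. If very few subjects are unknown, or all of them respond alike, the *unknown* coefficient may not be estimable in a logistic model. The treatment estimate is then about where deletion would have left it, so the change should do no worse than deletion.

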14.3 Safety Data

14.3.1 Displays of Adverse Events

Table 100: Overall Summary of Adverse Events, Safety Population*

	Group 1: Simultaneous Administration (N=X)		Group 2: Sequential Administration (N=X)		Group 3: IIV4 Only (N=X)	
	n	%	n	%	n	%
Subjects ^a with						
At least one local solicited adverse event	x	x	x	x	x	x
At least one systemic solicited adverse event	x	x	x	x	x	x
At least one unsolicited adverse event	x	x	x	x	x	x
At least one related unsolicited adverse event	x	x	x	x	x	x
Mild (Grade 1)	x	x	x	x	x	x
Moderate (Grade 2)	x	x	x	x	x	x
Severe (Grade 3)	x	x	x	x	x	x
Not yet assessed						
At least one severe (Grade 3) unsolicited adverse event	x	x	x	x	x	x
Related	x	x	x	x	x	x
Unrelated	x	x	x	x	x	x
Not yet assessed						
At least one serious adverse event ^b	x	x	x	x	x	x
At least one related, serious adverse event	x	x	x	x	x	x

Table 100: Overall Summary of Adverse Events, Safety Population *(continued)*

	Group 1: Simultaneous Administration (N=X)		Group 2: Sequential Administration (N=X)		Group 3: HIV4 Only (N=X)	
	n	%	n	%	n	%
Subjects ^a with						
At least one adverse event leading to early termination ^c	x	x	x	x	x	x
At least one medically attended adverse event	x	x	x	x	x	x
At least one new onset chronic medical condition	x	x	x	x	x	x
At least one potentially immune mediated medical condition	x	x	x	x	x	x
N = Number of subjects in the safety population. ^a Subjects are counted once for each category regardless of the number of events. ^b A listing of Serious Adverse Events is included in Table 126 ^c As reported on the Adverse Event eCRF						

Table 101: Number of Adverse Events Occurring in 5% of Subjects in Any Treatment Group by MedDRA® System Organ Class and Preferred Term, and Treatment Group - Safety Population

MedDRA System Organ Class	Preferred Term	Group 1: Simultaneous Administration (N=X)			Group 2: Sequential Administration (N=X)			Group 3: IIIV4 Only (N=X)			
		n	%	Events	n	%	Events	n	%	Events	
Serious Adverse Events											
All	All	x	x	x	x	x	x	x	x	x	x
SOC1	PT1	x	x	x	x	x	x	x	x	x	x
Etc.	Etc.	x	x	x	x	x	x	x	x	x	x
Other (Non-serious) Adverse Events											
All	All	x	x	x	x	x	x	x	x	x	x
SOC1	PT1	x	x	x	x	x	x	x	x	x	x
Etc	Etc	x	x	x	x	x	x	x	x	x	x
N = number of subjects in the safety population. n= number of subjects reporting event. Events = total frequency of events reported. MedDRA Version X.X.											

14.3.1.1 Solicited Adverse Events

Table 102: Number and Percentage of Subjects Experiencing Solicited Events with 95% Confidence Intervals by Symptom and Treatment Group (Safety Population) – Post Any Study Dose*

Symptom	Group 1: Simultaneous Administration (N=X)		Group 2: Sequential Administration (N=X)		Group 3: HIV4 Only (N=X)	
	n	% (95% CI)	n	% (95% CI)	n	% (95% CI)
Any Symptom	x	xx (xx-xx)	x	xx (xx-xx)	x	xx (xx-xx)
Any Systemic Symptom						
Fever						
Feverishness						
Fatigue						
Malaise						
Myalgia						
Arthralgia						
Headache						
Nausea						
Any Local Symptom						
Pain						
Tenderness						
Pruritus						
Ecchymosis						
Ecchymosis (measurement)						
Erythema						
Erythema (measurement)						
Induration/Swelling						

Table 102: Number and Percentage of Subjects Experiencing Solicited Events with 95% Confidence Intervals by Symptom and Treatment Group (Safety Population) – Post Any Study Dose (continued)

Symptom	Group 1: Simultaneous Administration (N=X)		Group 2: Sequential Administration (N=X)		Group 3: HV4 Only (N=X)	
	n	% (95% CI)	n	% (95% CI)	n	% (95% CI)
Induration/Swelling (measurement)						
N = Number of subjects in the Safety Population who received any dose. 95% CI estimated using Clopper-Pearson exact method						

Tables with similar format:

Table 103: Number and Percentage of Subjects Experiencing Solicited Events with 95% Confidence Intervals by Symptom and Treatment Group (Safety Population) – Post Study Dose 1*

[Footnote update] N = Number of subjects in the Safety Population who received the first dose.

Table 104: Number and Percentage of Subjects Experiencing Solicited Events with 95% Confidence Intervals by Symptom and Treatment Group (Safety Population) – Post Study Dose 2*

[Footnote update] N = Number of subjects in the Safety Population who received the second dose.

Table 105: Number and Percentage of Subjects Experiencing Solicited Events with 95% Confidence Intervals by Symptom and Treatment Group (Safety Population) – Post Study Dose 3*

[Footnote update] N = Number of subjects in the Safety Population who received the third dose.

Table 106: Logistic Regression Model to Evaluate the Relationship of Treatment with Reporting Any Local Event Post Any Study Dose (Safety Population) *

Model Parameter	Parameter Category	Parameter Estimate	SE	p-value	Odds Ratio	95%CI
Intercept	N/A	xxx.x	xxx.x	x.xxx	-	-
Treatment	Simultaneous Administration (reference)	-	-	-	-	-
	Sequential Administration	xxx.x	xxx.x	x.xxx	xx.x	xx.x-xx.x
	IIV4 Only	xxx.x	xxx.x	x.xxx	xx.x	xx.x-xx.x

N = number of subjects in the safety population.

Table with similar format:

Table 107: Logistic Regression Model to Evaluate the Relationship of Treatment with Reporting Any Systemic Event Post Any Study Dose (Safety Population) *

Table 108: Number and Percentage of Subjects Experiencing Solicited Events by Symptom, Maximum Severity and Treatment Group (Safety Population) – Post Any Study Dose*

Symptom	Severity	Group 1: Simultaneous Administration (N=X)		Group 2: Sequential Administration (N=X)		Group 3: IIV4 Only (N=X)	
		n	% (95% CI)	n	% (95% CI)	n	% (95% CI)
Any Symptom	None	x	xx (xx-xx)	x	xx (xx-xx)	x	xx (xx-xx)
	Mild						
	Moderate						
	Severe						
Any Systemic Symptom	None	x	xx (xx-xx)	x	xx (xx-xx)	x	xx (xx-xx)
	Mild						
	Moderate						
	Severe						
Fever	None						
	Mild						
	Moderate						
	Severe						
Feverishness	None						
	Mild						
	Moderate						
	Severe						
Fatigue	None						
	Mild						
	Moderate						
	Severe						
Malaise	None						
	Mild						

Table 108: Number and Percentage of Subjects Experiencing Solicited Events by Symptom, Maximum Severity and Treatment Arm (Safety Population) – Post Any Study Dose (continued)

Symptom	Severity	Group 1: Simultaneous Administration (N=X)		Group 2: Sequential Administration (N=X)		Group 3: HIV4 Only (N=X)	
		n	% (95% CI)	n	% (95% CI)	n	% (95% CI)
	Moderate						
	Severe						
Myalgia	None						
	Mild						
	Moderate						
	Severe						
Arthralgia	None						
	Mild						
	Moderate						
	Severe						
Headache	None						
	Mild						
	Moderate						
	Severe						
Nausea	None						
	Mild						
	Moderate						
	Severe						
Any Local Symptom	None						
	Mild						
	Moderate						
	Severe						

Table 108: Number and Percentage of Subjects Experiencing Solicited Events by Symptom, Maximum Severity and Treatment Arm (Safety Population) – Post Any Study Dose (continued)

Symptom	Severity	Group 1: Simultaneous Administration (N=X)		Group 2: Sequential Administration (N=X)		Group 3: HIV4 Only (N=X)	
		n	% (95% CI)	n	% (95% CI)	n	% (95% CI)
Pain	None						
	Mild						
	Moderate						
	Severe						
Tenderness	None						
	Mild						
	Moderate						
	Severe						
Pruritus	None						
	Mild						
	Moderate						
	Severe						
Ecchymosis	None						
	Mild						
	Moderate						
	Severe						
Ecchymosis (measurement)	None						
	Mild						
	Moderate						
	Severe						
Erythema	None						
	Mild						

Table 108: Number and Percentage of Subjects Experiencing Solicited Events by Symptom, Maximum Severity and Treatment Arm (Safety Population) – Post Any Study Dose (continued)

Symptom	Severity	Group 1: Simultaneous Administration (N=X)		Group 2: Sequential Administration (N=X)		Group 3: HIV4 Only (N=X)	
		n	% (95% CI)	n	% (95% CI)	n	% (95% CI)
	Moderate						
	Severe						
Erythema (measurement)	None						
	Mild						
	Moderate						
	Severe						
Induration/Swelling	None						
	Mild						
	Moderate						
	Severe						
Induration/Swelling (measurement)	None						
	Mild						
	Moderate						
	Severe						

N = Number of subjects in the Safety Population who received any study dose.
 95% CI estimated using Clopper-Pearson exact method
 Severity is the maximum severity reported over all solicited symptoms post dosing for each subject.

Tables with similar format:

Table 109: Number and Percentage of Subjects Experiencing Solicited Events by Symptom, Maximum Severity and Treatment Group (Safety Population) – Post Study Dose 1*

[Footnote Update] N = Number of subjects in the Safety Analysis Population who received the first study dose.

Table 110: Number and Percentage of Subjects Experiencing Solicited Events by Symptom, Maximum Severity and Treatment Group (Safety Population) – Post Study Dose 2*

[Footnote Update] N = Number of subjects in the Safety Analysis Population who received the second study dose.

Table 111: Number and Percentage of Subjects Experiencing Solicited Events by Symptom, Maximum Severity and Treatment Group (Safety Population) – Post Study Dose 3*

[Footnote Update] N = Number of subjects in the Safety Analysis Population who received the third study dose.

Table 112: Number and Percentage of Subjects Experiencing Solicited Events by Symptom, Severity, Day Post Dose, and Treatment Group (Safety Population) – Post Any Study Dose

Symptom	Severity	Pre-Dose		Post-Dose		Day 1		Day 2		Day 3		Day 4		Day 5		Day 6		Day 7		Day 8+	
		n	%	n	%	n	%	n	%	n	%	n	%	n	%	n	%	n	%	n	%
Group 1: Simultaneous Administration (N=X)																					
Any Symptom	None																				
	Mild																				
	Moderate																				
	Severe																				
Any Systemic Symptom	None																				
	Mild																				
	Moderate																				
	Severe																				
Fever	None																				
	Mild																				
	Moderate																				
	Severe																				
Feverishness	None																				
	Mild																				
	Moderate																				
	Severe																				
Fatigue	None																				
	Mild																				
	Moderate																				
	Severe																				
Malaise	None																				
	Mild																				

Table 112: Number and Percentage of Subjects Experiencing Solicited Events by Symptom, Severity, Day Post Study Vaccination, and Treatment Arm (Safety Population) – Post Any Study Dose (continued)

Symptom	Severity	Pre-Dose		Post-Dose		Day 1		Day 2		Day 3		Day 4		Day 5		Day 6		Day 7		Day 8+		
		n	%	n	%	n	%	n	%	n	%	n	%	n	%	n	%	n	%	n	%	
	Moderate																					
	Severe																					
Myalgia	None																					
	Mild																					
	Moderate																					
	Severe																					
Arthralgia	None																					
	Mild																					
	Moderate																					
	Severe																					
Headache	None																					
	Mild																					
	Moderate																					
	Severe																					
Nausea	None																					
	Mild																					
	Moderate																					
	Severe																					
Any Local Symptom	None																					
	Mild																					
	Moderate																					
	Severe																					
Pain	None																					

Table 112: Number and Percentage of Subjects Experiencing Solicited Events by Symptom, Severity, Day Post Study Vaccination, and Treatment Arm (Safety Population) – Post Any Study Dose (continued)

Symptom	Severity	Pre-Dose		Post-Dose		Day 1		Day 2		Day 3		Day 4		Day 5		Day 6		Day 7		Day 8+		
		n	%	n	%	n	%	n	%	n	%	n	%	n	%	n	%	n	%	n	%	
	Mild																					
	Moderate																					
	Severe																					
Tenderness	None																					
	Mild																					
	Moderate																					
	Severe																					
Pruritus	None																					
	Mild																					
	Moderate																					
	Severe																					
Ecchymosis	None																					
	Mild																					
	Moderate																					
	Severe																					
Ecchymosis (measurement)	None																					
	Mild																					
	Moderate																					
	Severe																					
Erythema	None																					
	Mild																					
	Moderate																					
	Severe																					

Table 112: Number and Percentage of Subjects Experiencing Solicited Events by Symptom, Severity, Day Post Study Vaccination, and Treatment Arm (Safety Population) – Post Any Study Dose (continued)

Symptom	Severity	Pre-Dose		Post-Dose		Day 1		Day 2		Day 3		Day 4		Day 5		Day 6		Day 7		Day 8+		
		n	%	n	%	n	%	n	%	n	%	n	%	n	%	n	%	n	%	n	%	
Erythema (measurement)	None																					
	Mild																					
	Moderate																					
	Severe																					
Induration/Swelling	None																					
	Mild																					
	Moderate																					
	Severe																					
Induration/Swelling (measurement)	None																					
	Mild																					
	Moderate																					
	Severe																					
[repeat for all treatment groups]																						
N = Number of subjects in the Safety Analysis Population who received the specified dose. Severity is the maximum severity reported post dosing for each subject for each day.																						

Tables with similar format:

Table 113: Number and Percentage of Subjects Experiencing Solicited Events by Symptom, Severity, Day Post Dose, and Treatment Group (Safety Population) – Post Study Dose 1

Table 114: Number and Percentage of Subjects Experiencing Solicited Events by Symptom, Severity, Day Post Dose, and Treatment Group (Safety Population) – Post Study Dose 2

Table 115: Number and Percentage of Subjects Experiencing Solicited Events by Symptom, Severity, Day Post Dose, and Treatment Group (Safety Population) – Post Study Dose 3

Table 116: Comparison of the Number and Percentage of Subjects Experiencing Solicited Systemic Events by Dose and Treatment Group – Safety Population

		Subjects with No Symptoms	Subjects with Mild or Greater Symptoms	Total Number of Subjects n (Percent) [p-value*]
Study Dose 1 vs Study Dose 2				
Group 1: Simultaneous Administration (N=X)	Subjects with No Symptoms	x (%)	x (%)	x (%)
	Subjects with Mild or Greater Symptoms	x (%)	x (%)	x (%)
	Total Number of Subjects	x (%)	x (%)	x (100%) [0.xxx]
Group 2: Sequential Administration (N=X)	Subjects with No Symptoms	x (%)	x (%)	x (%)
	Subjects with Mild or Greater Symptoms	x (%)	x (%)	x (%)
	Total Number of Subjects	x (%)	x (%)	x (100%) [0.xxx]
Study Dose 1 vs Study Dose 3				
Group 2: Sequential Administration (N=X)	Subjects with No Symptoms	x (%)	x (%)	x (%)
	Subjects with Mild or Greater Symptoms	x (%)	x (%)	x (%)
	Total Number of Subjects	x (%)	x (%)	x (100%) [0.xxx]
Study Dose 2 vs Study Dose 3				
Group 2: Sequential Administration (N=X)	Subjects with No Symptoms	x (%)	x (%)	x (%)
	Subjects with Mild or Greater Symptoms	x (%)	x (%)	x (%)
	Total Number of Subjects	x (%)	x (%)	x (100%) [0.xxx]

Note: Denominators for percentages are the number of subjects in the safety population who received both the first and second study dose. Subjects who did not receive both indicated doses are not included in this table. [x] subjects did not receive the second dose and [x] subjects did not receive the third dose.
* P-value is calculated from McNemar's test for each treatment group.

Table with similar format:

Table 117: Comparison of the Number and Percentage of Subjects Experiencing Solicited Local Events by Dose and Treatment Group – Safety Population

